**Note: Do not include a list of citations in this section. Please limit this section to no more than 300 words.**

Alcoholism is the third leading cause of preventable death in the US, accounting for 80,000 deaths annually. Almost 18 million US adults have alcohol use disorder (AUD); however, approved medications for the treatment of AUD has shown limited effectiveness.

Zonisamide (ZON), a broad spectrum anticonvulsant, has proven to be more effective than a placebo in reducing alcohol intake in individuals with alcohol dependence. ZON’s mechanism of action seems to be quite distinct from currently approved anti-alcoholism medications, which holds promise for treatment of individuals who are not responsive to conventional medications.

However, much remains unknown about ZON's therapeutic mechanisms and ZON's efficacy in treating patients with a diagnosis of AUD.

To fill in these gaps, we will conduct a double-blind randomized controlled study that assesses ZON's treatment mechanisms and effectiveness in reducing alcohol consumption in patients with AUD. Participants will be randomized to one of two conditions: 1) treatment with ZON and a computerized alcohol reduction and medication compliance program called *Take Control* (TC); 2) treatment with a placebo (PLC) and TC. To understand the neurobiology behind ZON's potential therapeutic effects on AUD, fMRI will be acquired at baseline (pre-treatment) and near the end of study treatment and used to compare the brain activity of the ZON+TC versus PLC+TC group while they perform an alcohol and emotional-word Stroop task, as well as an alcohol related cues task.

Compared to the PLC+TC group, we hypothesize that the ZON+TC group will: 1) have significantly greater reductions in alcohol consumption by the end of a 12-week treatment period; 2) show enhanced midbrain-frontal connectivity while performing the Stroop task during an fMRI procedure; and 3) decreased limbic and prefrontal activity during an alcohol cues task.

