### Randomization

Participants who continue to be eligible for the study following the in-clinic screening will be randomized to one of two treatment conditions: 1) Zonisimaide and *Take Control* (TC) computerized program; 2) a placebo and TC. An adaptive randomization will be used, where gender, heavy drinking, handedness, and smoking status will be variable levels.

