#### Data Analysis

1. Demonstrate that ZON will attenuate changes resulting from performance on alcohol-word and negative-word Stroop tasks in the activity of frontal-parietal and midbrain regions and the connectivity to networks associated with these regions in AUD subjects. Our working hypothesis is that midbrain activity will be lower in ZON treated subjects than in placebo subjects following performance on alcohol and negative emotion Stroop task, which will occur in association with enhanced mid-brain-frontal connectivity and increased synchrony.

Fixed effects models will be used to analyze data for brain activation in regions of interest, with treatment group as a between group factor and Stroop task type and order of stimuli presentation will be within subject factors. Regions of interest will include parahippocampal gyri, midbrain substantia nigra and red nucleus, dorso-lateral prefrontal cortex, and cerebellum.

Connectivity will be assessed using the Free Surfer analysis described below. Seeds will be used for the dorsolateral prefrontal cortex and the midbrain (substantia nigra) following Muller-Oehring et al. (2013).

2. Demonstrate that ZON administration attenuates the enhanced regional brain activity and craving- induced by exposure to alcohol related cues in AUD subjects. Our hypothesis is that exposure to alcohol-related cues will increase brain activity in select limbic and prefrontal areas to a lesser degree in ZON as compared to placebo treated AUD subjects.

Fixed effects models will be used to analyze data for brain activation in regions of interest, with treatment group as a between group factor and stimulus type and order of stimuli presentation was within subject factors. Regions of interest, based on the meta-analysis of Schacht et al. (2013), will include the ventral striatum, medial prefrontal cortex, and the anterior cingulate cortex.

3. Demonstrate that the ZON induced changes in brain activity are predictive of reduced ethanol consumption.

Logistic regression analysis will be used to evaluate zonisamide-induced decreases in the BOLD response in the ventral striatum and the medial prefrontal cortex as predictors of complete abstinence or reduction to safe drinking levels (defined as consumption of no more than more than 2 standard drinks per day) during study weeks 10 to 12.

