4. Replicate the finding that ZON will reduce alcohol consumption in AUD subjects. Our working hypothesis is that the drinks consumed per day and percent days drinking will be significantly lower in AUD subjects receiving ZON than in those treated with placebo.

Drinking measures derived from the TLFB data will include the percent days drinking, the number of drinks consumed per day, and the percent days heavy drinking. Heavy drinking will be defined as 4 or more drinks per day for women and 5 or more drinks per day for men.

Alcohol consumption measures will be analyzed using repeated measures mixed models analysis using SAS PROC MIXED (ver 9.3, SAS Institute, Cary, NC) with baseline values for these measures used as covariates. Comparisons will be made for data obtained for the 12 week treatment period for the two conditions.

5. Demonstrate that ZON administration will reduce impulsive and risk taking behaviors. Our working hypothesis is that the ZON will decrease risk taking behavior as assessed using the Rogers Risk Task and the Balloon Analog Risk Task and impulsivity as measured using the Go/NoGo and the Continuous Performance Test (CPT).

Repeated measures mixed models analysis will be used to analyze data obtained for pre-randomization and week 12 data for the Rogers Risk Task, the Balloon Analog Risk Task, the Go/NoGoTask, the CPT, and Go/No Go. Model generated group least square means values for week 12 will be compared using student t-tests.

[name] will provide statistical consultation. He will not have access to identifiable information and will not have any contact with study participants.

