#### **Analysis**

The images will be analyzed using FSL 4.1.1 with the FMRI Expert Analysis Tool (FEAT) v5.98 (Smith et al., 2004; Jenkinson et al., 2012). FSL's general linear model will be used to

model each subject's BOLD response to each explanatory variable (EV). The fMRI data will be co-registered to MNI space and regions of significant activation will be determined through using the Harvard-Oxford Structural Atlas included with FSL (Makris et al., 2006; Frazier et al., 2005; Desikan et al., 2006; Goldstein et al., 2007). In second and third level analyses, we will use cluster thresholding with a Z threshold of 2.3 and a cluster p threshold of 0.05. We will use a fixed effects model for these analyses. All analyses of the fMRI data will include active task > control condition contrasts as well as control > active task contrasts as a reality check.

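### As written, Aim 5 takes almost nothing from its baseline data, Aims 1 and 2 do not say how the baseline scan enters, and no efficacy model carries the randomisation factors

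*Combined protocol and SAP*

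**What the plan says.** All places are in the combined protocol and SAP.

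- **Section L, Data Analysis, Aim 5** (Rogers Risk Task, Balloon Analog Risk Task, Go/NoGo, CPT): "Repeated measures mixed models analysis will be used to analyze data obtained for pre-randomization and week 12 data". The comparison is then "Model generated group least square means values for week 12 will be compared using student t-tests". No baseline covariate or equal-baseline constraint is mentioned.
- **Aim 4** (drinking measures): a repeated measures mixed model "with baseline values for these measures used as covariates".
- **Aim 1** (Stroop imaging): a model "with treatment group as a between group factor and Stroop task type and order of stimuli presentation will be within subject factors". **Aim 2** (alcohol cues imaging): a model "with treatment group as a between group factor and stimulus type and order of stimuli presentation was within subject factors". Neither lists a session, change or baseline-scan term.
- **Section G, Study Summary**: "fMRI will be acquired at baseline (pre-treatment) and near the end of study treatment and used to compare the brain activity" of the two arms.
- **Imaging Acquisition and Processing, Analysis**, on the second- and third-level imaging analyses: "We will use a fixed effects model for these analyses".
- **Randomization**: "An adaptive randomization will be used, where gender, heavy drinking, handedness, and smoking status will be variable levels". No efficacy model in Aims 1 to 5 names any of these four. The only adjustment of this kind is in Safety Analysis, where a logistic regression adjusts for a single stratification factor that is not named.

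**The concern.** The plan accepts baseline adjustment in Aim 4 but does not carry it through. In a two-occasion model that treats baseline as a response and leaves the baseline means free, the week-12 contrast is not adjusted for chance baseline differences between the arms. With complete data it is exactly the raw week-12 difference. The plan collects the baseline value and then makes almost no use of it in the comparison that matters.

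For Aims 1 and 2 the gap is of another kind. With two scans per participant and no session term, the group effect could mean week 12 alone, a change, or both scans pooled. These are different estimands with different precision.

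Leaving the balancing factors out of the model gives up whatever outcome variance they explain. It can also make the test's true level differ from the nominal one. At about 40 evaluable participants per arm, precision is worth having where the data are already collected.

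**Working it through.** **1. The plan's own figures.** Inputs from Power Analysis: 40 per arm, alpha 0.05, effect sizes 0.74 (drinks per day) and 0.7 (ventral striatum), 20% dropout. Sidedness is not stated; two-sided reproduces the figures. Noncentral t, 78 df, noncentrality d × √(40/2):

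- d = 0.74: 0.74 × 4.472 = 3.31, power 0.905 (stated 0.9).
- d = 0.7: 0.7 × 4.472 = 3.13, power 0.871, or 0.879 by the normal approximation (stated 0.88).
- 40 / (1 − 0.2) = 50 randomised per arm, as stated.
- CPT: no effect size is given; the stated power of 0.97 solves to d = 0.870.

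These are unadjusted two-sample calculations, and they stand.

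**2. The Aim 5 contrast.** Let r be the correlation between baseline and week 12. It is not given, so 0.3, 0.5 and 0.7 are assumed. With free baseline means, 50 baselines and 40 week-12 values per arm, the fitted week-12 mean in an arm is ȳ₄₀ + β(b̄₅₀ − b̄₄₀). Its variance is

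σ²(1 − r²)/40 + σ²r²/50 = (σ²/40)(1 − 0.2r²).

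The standard error ratio to the raw difference is √(1 − 0.2r²) = 0.991, 0.975, 0.950. A baseline covariate gives about √(1 − r²), slightly less favourable in finite samples. The covariate reductions below come from simulation (40,000 replicates; SD 0.215/0.194/0.161 against 0.223/0.223/0.224 raw).

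| Assumed r | SE reduction, free baseline means | SE reduction, baseline covariate | d detectable at 90% power: free means | covariate |
|---|---|---|---|---|
| 0.3 | 1% | 4% | 0.727 | 0.700 |
| 0.5 | 3% | 13% | 0.715 | 0.636 |
| 0.7 | 5% | 28% | 0.697 | 0.524 |

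Week 12 alone needs d = 0.734. In one simulated complete data set (r = 0.5), the free-means contrast and the raw difference were identical at −0.682 (SE 0.207). The covariate model gave −0.722 (SE 0.175) and the constrained-baseline model −0.722 (SE 0.173).

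**3. Power with a baseline covariate** (effect d/√(1 − r²), 77 df; r = 0.3/0.5/0.7):

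- d = 0.7, a between-subject ROI comparison: 0.871 unadjusted, 0.900/0.946/0.991 adjusted. At r = 0.1 and 0.2 it is only 0.874 and 0.884.
- d = 0.870 (CPT): 0.97 unadjusted, 0.981/0.993/above 0.999 adjusted.

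**4. Why the use of the two scans must be stated.** A group effect averaged over both scans has expected size (0 + 0.7)/2 = 0.35 in week-12 SD units, half the treatment effect. A change score has variance ratio 2(1 − r) and power 0.743/0.871/0.979 at d = 0.7, so it beats week 12 alone only when r exceeds 0.5.

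**5. Omitted randomisation factors.** Let R² be the outcome variance they explain (assumed 0.1 and 0.2). With exact balance at 50 per arm, then random loss to 40, the true variance of the difference is (1 − 0.8R²) times the value that the unadjusted test estimates: 0.92 and 0.84. Results at R² = 0.1/0.2:

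| Allocation (assumed) | True alpha, unadjusted test |
|---|---|
| Exact balance, then random loss | 0.041/0.033 |
| Deterministic minimisation | 0.042/0.033 |
| Minimisation, 0.8 biased coin | 0.043/0.036 |
| Simple randomisation | 0.053/0.050 |

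At d = 0.7 under exact balance, unadjusted power is 0.879/0.893. Adjusted power by formula is 0.903/0.932.

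**6. Cost if the factors explain nothing** (d = 0.7, r = 0.3). Counting only degrees of freedom, power goes from 0.8998 to 0.8994. That omits the variance added by factor imbalance among completers. Simulated with 20% random loss and four two-level factors at assumed prevalences, power went from 0.894 to 0.888 (deterministic minimisation), 0.897 to 0.892 (biased coin) and 0.896 to 0.878 (simple randomisation). A second set of runs gave losses of 0.3 to 0.5 points under minimisation and 1.3 under simple allocation. The range is therefore about 0.3 to 2 points. Adjustment breaks even at R² of about 0.02 under minimisation and 0.05 under simple randomisation.

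**The case against.** **Baseline is already in Aim 5, and the plan does not exclude a constrained fit.** Both statements are true. A reader might infer that Aim 5 ignores baseline; it does not. But the week-12 contrast benefits materially only if the constraint is imposed, and the plan does not impose it. This stands as a gap to close.

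**A pre-post comparison is implied for imaging.** This has force. The Study Summary uses both scans to compare the arms, and Aim 3 takes drug-related reductions in BOLD signal as predictors. A reader might infer that the baseline scans go unused; the documents do not show that. What is missing is the term that says how they are used. The power figures in step 3 also apply only to a between-subject ROI comparison, and neither they nor the alpha results carry over to the fixed-effects imaging levels.

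**The powered outcomes barely move.** This is partly right. CPT gains 1 to 3 points on 0.97. Aim 4 already has baseline covariates: at d = 0.74 and r = 0.5 its power is 0.965, rising to 0.972 or 0.978 if the factors explain a further 5 or 10% of residual variance. The other Aim 5 tasks have no power figure at all, so the smaller detectable effect matters more there.

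**Adding four factors is not free.** This stands. The cost in step 6 is small but real, R² is unknown, and the documents give no levels for the factors. Handedness may leave very few people in one level.

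**Conclusion.** The point holds as one of precision and specification, and is worth acting on. The firmest part is Aim 5: without an equal-baseline constraint the standard error falls by 1 to 5%, where a baseline covariate would give 4 to 28%, over assumed r of 0.3 to 0.7. The imaging part is softer and is mainly a request to state the estimand, so that the scans are not pooled. The randomisation-factor part holds for the between-arm models, with little to expect in Aim 4.

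Two stronger conclusions are not supported. A reader might infer that the trial is underpowered or that a stated power is wrong; the 0.9 and 0.88 reproduce without any adjustment. A reader might also infer that the unadjusted tests are reliably conservative. That depends on the balancing algorithm, which is not given, on the variance the factors explain and on dropout; under simple randomisation alpha stays near 0.05.

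Every r, R², factor prevalence and factor coding used here is an assumption.

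**What to change.** Changes to the SAP text, to be made before unblinding:

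1. **Aim 5.** Analyse each task's week-12 value with its own baseline as covariate, as Aim 4 already does, or fit a group-by-time model with baseline means constrained equal. The covariate version needs a rule for participants without a baseline value; the constrained model keeps them.
2. **Aims 1 and 2.** State that the between-subject ROI comparison uses the week-12 value adjusted for the baseline scan, or the constrained group-by-session model, so that the two scans are not pooled.
3. **Aims 1, 2, 4 and 5.** Add gender, heavy drinking, handedness and smoking status to the between-arm models. Define the levels of each, and give a rule for sparse levels such as handedness. Name the factor meant in the safety regression.

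This needs no new data and no change to sample size. The cost is about 0.3 to 2 percentage points of power if the factors explain nothing, depending on the randomisation algorithm. If every factor has two levels, which is an assumption, the baseline and the four factors together use five of 78 degrees of freedom at 40 per arm; other codings use more.

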#### Imaging Acquisition and Processing:

#### **BOLD RESPONSE- Image Acquisition**

Functional images will be acquired on a Siemens Prisma 3T scanner using a 64-channel phased array headcoil. Blood oxygenation level-dependent (BOLD) contrast will be measured using a gradient echo-planar T2\* weighted imaging sequence (TR = 2000 ms, TE = 28 ms, EPI factor = 47). The images will contain 36 axial slices and each slice will be 64 x 64 pixels. The voxel size will be 3 mm x 3 mm x 3 mm. T1-weighted structural images will also be obtained in the same session along with a brief EPI sequence acquired with oblique slices to ensure the integrity of right and left throughout image format conversion. All images will be converted to FSL-NIfTI format prior to our model-based analysis and the integrity of left and right for each subject will be confirmed.

#### **Analysis**

The images will be analyzed using FSL 4.1.1 with the FMRI Expert Analysis Tool (FEAT) v5.98 (Smith et al., 2004; Jenkinson et al., 2012). FSL's general linear model will be used to

model each subject's BOLD response to each explanatory variable (EV). The fMRI data will be co-registered to MNI space and regions of significant activation will be determined through using the Harvard-Oxford Structural Atlas included with FSL (Makris et al., 2006; Frazier et al., 2005; Desikan et al., 2006; Goldstein et al., 2007). In second and third level analyses, we will use cluster thresholding with a Z threshold of 2.3 and a cluster p threshold of 0.05. We will use a fixed effects model for these analyses. All analyses of the fMRI data will include active task > control condition contrasts as well as control > active task contrasts as a reality check.

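### Cluster thresholding at Z 2.3 does not assure a 5% error rate for zonisamide-versus-placebo brain maps unless spatial noise is close to Gaussian-shaped; a permutation test of arm labels would

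*Combined protocol and SAP*

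**What the plan says.** All of this is in Section L of the combined protocol and SAP.

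- Under Imaging Acquisition and Processing, Analysis, the software is fixed: "The images will be analyzed using FSL 4.1.1 with the FMRI Expert Analysis Tool (FEAT) v5.98".
- For second- and third-level analyses the same paragraph says "we will use cluster thresholding with a Z threshold of 2.3 and a cluster p threshold of 0.05", followed by "We will use a fixed effects model for these analyses".
- Significant areas are then given anatomical names: "regions of significant activation will be determined through using the Harvard-Oxford Structural Atlas included with FSL".
- The contrasts listed there are "active task > control condition contrasts as well as control > active task contrasts as a reality check".
- The treatment comparison is described under Data Analysis, aims 1 and 2. These specify models for regions of interest "with treatment group as a between group factor". For the cue task the regions "will include the ventral striatum, medial prefrontal cortex, and the anterior cingulate cortex". Aim 1 has its own list of named regions.

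The Analysis paragraph names no permutation test, smoothing kernel, search mask or check of the cluster error rate.

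**The concern.** A random-field cluster p-value asks how large a blob of above-threshold voxels would arise by chance. It answers from one smoothness figure, estimated from neighbouring voxels, and treats spatial correlation as falling off like a Gaussian curve. If correlation has a longer tail, the smoothness estimate misses it and chance clusters are larger than the formula allows. A low cluster-forming threshold makes this worse, because large and diffuse clusters carry the inference.

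Aims 1 and 2 make regional claims about zonisamide. The plan names active areas from an atlas and has arm as the between-group factor, so it is reasonable to infer that zonisamide-versus-placebo maps will be produced and read under this rule. A chance cluster in such a map could be reported as a drug effect. If it is large enough to cover several atlas labels, the location is uncertain too.

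**Working it through.** **The plan's own figures.** The cluster p of 0.05 is a setting, so there is nothing to reproduce for it. The power statements do reproduce. With 40 per group and effect size 0.7, power = Φ(0.7/√(2/40) − 1.96) = 0.879 (stated 0.88). With 0.74 it is 0.911, or 0.905 using the t distribution (stated 0.9). Neither figure bears on map-level error.

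**Inputs from the documents.** Z 2.3; cluster p 0.05; 3 mm voxels; 64 × 64 × 36 matrix; 40 per group at week 12.

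**Assumptions.** A random-field cluster p; stationary noise; an ellipsoid for the brain; and the shape of the spatial correlation.

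**Formula.** With threshold u, V voxels in the mask and R resels (V divided by the product of the three FWHMs in voxels):

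- E[m] = R (4 ln 2)^1.5 (2π)^−2 (u² − 1) exp(−u²/2)
- β = {Γ(2.5) E[m] / (V [1 − Φ(u)])}^(2/3)
- p(k) = 1 − exp{−E[m] exp(−β k^(2/3))}

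**Worked example.** V = 47,184 and FWHM 10 mm.

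- R = 47,184/(10/3)³ = 1,274.
- The one-sided voxel p at Z 2.3 is 0.0107, so about 506 voxels exceed the threshold by chance.
- E[m] = 45.4 and β = 0.242.
- Setting p = 0.05 gives k = [ln(45.4/0.0513)/0.242]^1.5, about 148 voxels (4.0 mL).
- At Z 3.1 (voxel p 0.00097) the same steps give about 40 voxels (1.1 mL).

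**Null simulation on the plan's matrix.** There were 600 maps per setting, with smoothness estimated from lag-1 correlation in each map. The table shows the proportion with at least one significant cluster in one direction.

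| Assumed spatial correlation | Z 2.3 | Z 3.1 |
|---|---|---|
| Gaussian, FWHM 8 / 10 / 12 mm | 2.0 / 2.5 / 1.8% | 2.5 / 2.8 / 1.8% |
| 10% weight in a 12 mm exponential tail | 8.3% | 3.0% |
| 20% | 15.3% | 5.8% |
| 30% | 28.3% | 7.3% |
| 40% | 37.0% | 10.5% |
| 40%, wider core, 16 mm tail | 35.2% | 11.2% |
| 50%, 14 mm tail | 47.2% | 15.8% |

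If the true rate were 5%, the Monte Carlo standard error would be √(0.05 × 0.95/600) = 0.9 percentage points, so even 8.3% is clearly above nominal.

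**Second, separate simulation.** This used 64 × 64 × 48, 55,536 voxels and 400 maps per setting, which is more slices than the plan's 36. Gaussian noise gave about 2% at Z 2.3. Weights of 20 / 35 / 50% in a 10 mm tail gave 20 / 33 / 53% at Z 2.3 and 8 / 12 / 17% at Z 3.1.

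**Permutation check.** Arm labels were permuted on two-sample t maps with 40 per arm, a 35% tail, a reduced grid and 99 permutations. This gave 4 rejections in 100 trials, exact 95% interval about 1 to 10%.

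**Fixed effects, taken separately.** Suppose the omitted between-subject variance is r times the variance the model does use. Null Z values are then inflated by √(1 + r), and the voxel p at Z 2.3 becomes 1 − Φ(2.3/√(1 + r)), for example 0.0198 at r = 0.25 and 0.0519 at r = 1. With Gaussian noise (10 mm, 200 maps each), the map error was 6.5, 18.5, 58.5 and 95% at r = 0.1, 0.25, 0.5 and 1. The first of these has a standard error of 1.7 points and is not clearly above 5%. The documents do not give r.

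**The case against.** **The size rests on assumed tails.** This stands. The documents give no noise shape, kernel or mask. Under Gaussian-shaped noise the rule is conservative, so a very slight tail need not push it past 5%. A reader might infer that false positives in this trial will run far above 5%. The documents do not support that; they leave the rate unknown.

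**Aims 1 and 2 are tested in named regions.** This also stands. The aims specify region-of-interest models, the imaging power statement is for the ventral striatum, and the cluster rule need not govern those tests. A reader might infer that the main imaging hypotheses are compromised by this rule. The text does not show that. Neither whole-brain maps nor arm contrasts are named in the cluster paragraph; both are inferences.

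**Two directions at 5% each.** A reader might infer that the paired contrasts are read at about 10% (1 − 0.95² = 9.75%). The text does not support this. Both contrasts are task against control, not arm against arm, and the reverse one is run only as a check: "active task > control condition contrasts as well as control > active task contrasts as a reality check".

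**The fixed effects model may be the larger defect.** It may be, depending on r. That does not remove the present point, but it does mean that a stricter Z cannot be the whole remedy.

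**The permutation check is thin.** A hundred trials in one setting is weak confirmation. The main support is the argument: if arm has no effect, labels that respect the allocation scheme are exchangeable whatever the noise shape.

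**Conclusion.** The nominal 5% is not assured for map-level zonisamide-versus-placebo findings. Two simulations agree on direction: about 2% with Gaussian-shaped noise, and about 8-53% at Z 2.3 under the long tails assumed. At Z 3.1 the long-tailed range is about 3-17%, so raising the threshold reduces the dependence on noise shape without removing it. The figures are illustrative. They rest on a random-field cluster p inferred from the software, an ellipsoid mask, stationary noise and assumed tail weights of 10-50%. The conclusion does not reach the pre-specified region-of-interest tests. It is a weakness in how exploratory maps would be read, and worth correcting because correction is cheap.

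**What to change.** Add the following to the Analysis paragraph.

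1. For any zonisamide-versus-placebo map, significance comes from permuting arm labels across subjects, using maximum cluster size or threshold-free cluster enhancement, about 5,000 permutations, two-sided 0.05 for the map.
2. The input is one summary map per participant, so that between-subject variation enters the test. The fixed effects statement should not apply to these maps.
3. The permutation scheme respects the adaptive-randomization factors listed under Randomization: gender, heavy drinking, handedness and smoking. If each has two levels (the plan does not say), there are 2⁴ = 16 cells for about 80 completers, or 5 per cell on average. The plan should therefore say how sparse cells are handled.
4. Any parametric cluster map is labelled descriptive, at Z 2.3 or Z 3.1.
5. State the smoothing kernel and search mask.

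The cost is computer time and a few sentences, with no new data. The downside is that fewer diffuse clusters will reach significance.
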